 - For Cycles 2+, cefixime will be administered on Days -1 through 8 and Days 20-21.

Days 27 and 28 of Cycle 1 are the same as Days -1 and 0 of Cycle 2. Days 20 and 21 of Cycles 2+ are the same as Days -1 and 0 of subsequent cycles.

NOTE: Once PCP Prophylaxis begins on Cycle 1 Day 8, patient should continuously receive PCP prophylaxis per the prescribed schedule until the end of treatment. See [Section 5.1](#) for more details.

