5.0 TREATMENT PROGRAM

5.1 Overview of Treatment Plan

Cycle 1							
Cycle Day							
1	6	8	9	10	11	12	28
Cefixime (Days 6 – 15, 27 – 28) ----->							
		TEMO	TEMO	TEMO	TEMO	TEMO	Eval
		IRIN	IRIN	IRIN	IRIN	IRIN	
Pevonedistat		Pevonedistat		Pevonedistat		Pevonedistat	
		PCP prophylaxis					
IRIN: Irinotecan; TEMO: temozolomide							

Cycle 2 and beyond							
Cycle Day							
-1	0	1	2	3	4	5	21
Cefixime (Days -1 to 8, 20 – 21) ----->							
		TEMO	TEMO	TEMO	TEMO	TEMO	Eval
		IRIN	IRIN	IRIN	IRIN	IRIN	
		Pevonedistat		Pevonedistat		Pevonedistat	
		PCP prophylaxis					
IRIN: Irinotecan; TEMO: temozolomide							

See [Appendix XIII](#) for Therapy Delivery Maps for Cycle 1 and all subsequent cycles.

A cycle of therapy is considered to be 28 days for Cycle 1 and 21 days for Cycle 2 and subsequent cycles. Therapy will be discontinued if there is evidence of progressive disease or drug related dose-limiting toxicity that requires removal from protocol therapy. Patients may continue on protocol therapy for up to 17 cycles (approximately 12 months).

Pevonedistat will be administered intravenously over 60 minutes on Days 1, 8, 10, and 12 of Cycle 1 and on Days 1, 3, and 5 of Cycles 2+ (starting dose is 15 mg/m² [Dose Level 1]).

Cefixime will be administered starting at least two days prior to the start of irinotecan, during, and 3 days after the last dose of irinotecan of each cycle for a total of at least 10 days.

- For Cycle 1, cefixime will be administered on Days 6-15 and Days 27-28.
- For Cycles 2+, cefixime will be administered on Days -1 through 8 and Days 20 through 21.

Days 27 and 28 of Cycle 1 are the same as Days -1 and 0 of Cycle 2. Days 20 and 21 of Cycles 2+ are the same as Days -1 and 0 of subsequent cycles.

Drug doses should be adjusted based on the BSA calculated from height and weight measured within 7 days prior to the beginning of each cycle.

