5.3 Criteria for Starting Subsequent Cycles

After Cycle 1 which is 28 days, a cycle may be repeated every 21 days if the patient has at least stable disease and has again met laboratory parameters as defined in the eligibility section, [Section 4.0](#) or eligible to continue agent administration per the requirements in [Section 6.0](#).

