8	99 th	119	120	121	122	123	125	125	82	82	83	83	84	85	86
9	99 th	121	121	123	124	125	127	127	83	83	84	84	85	86	87
10	99 th	123	123	125	126	127	129	129	84	84	85	86	86	87	88
11	99 th	125	125	126	128	129	130	131	85	85	86	87	87	88	89
12	99 th	127	127	128	130	131	132	133	86	86	87	88	88	89	90
13	99 th	128	129	130	132	133	134	135	87	87	88	89	89	90	91
14	99 th	130	131	132	133	135	136	136	88	88	89	90	90	91	92
15	99 th	131	132	133	134	136	137	138	89	89	90	91	91	92	93
16	99 th	132	133	134	135	137	138	139	90	90	90	91	92	93	93
≥17	99 th	133	133	134	136	137	138	139	90	90	91	91	92	93	93

Instructions for using this BP Chart:

1. Measure the patient's blood pressure using an appropriate size cuff.
2. Select appropriate chart for a female or male patient.
3. Using the "age" row and "height" column determine if the BP is within the ULN.

This table was taken from "The Fourth Report on the Diagnosis, Evaluation, and Treatment of High Blood Pressure in Children and Adolescents" PEDIATRICS Vol. 114 No. 2 August 2004, pp. 555-576.

APPENDIX XIII-A: THERAPY DELIVERY MAPS (TDMS) FOR CYCLE 1

Therapy Delivery Map – Cycle 1		Accession #
This Therapy Delivery Map (TDM) relates to Cycle 1. Cycle 1 lasts 28 days. This TDM can be used for all dose levels of pevonedistat. Please record the dose level below. This TDM is intended to serve as a tool to assist in scheduling the required observations for the study; the schedule indicated in the chart below should be considered an example. The actual schedule must comply with the timing of required observations per Section 8 of the protocol.		Patient COG ID number
This form is to be completed and uploaded into RAVE at the end of every cycle.		Institution

Criteria to start each cycle are listed in [Section 5.3](#). Extensive treatment details are in [Section 5.1](#). This TDM is on 2 pages.

DRUG	ROUTE	DOSAGE	DAYS	IMPORTANT NOTES
Pevonedistat IND # 136078	IV over 60 minutes	Dose Level -1: 10 mg/m ² Dose Level 1: 15 mg/m ² Dose Level 2: 20 mg/m ² Dose Level 3: 25 mg/m ² Dose Level 4: 35 mg/m ²	1, 8, 10, 12	Administer alone on Day 1. Administer immediately after irinotecan on Days 8, 10, and 12. The dose level will be assigned via OPEN at the time of study enrollment.
Cefixime	PO	8 mg/kg/dose daily	6-15, 27-28	Maximum dose is 400 mg/day.
Temozolamide (TEMO)	PO	100 mg/m ² /dose daily	8-12	Maximum dose is 200 mg/day. See Appendix IV for oral capsules dosing nomogram.

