NOTE: PCP prophylaxis should start on Cycle 1 Day 8, given twice daily for 3 consecutive days a week (i.e., BID Friday, Saturday, Sunday), every week or per institutional practice, until the end of protocol therapy. See [Section 5.1](#) for details.

Assigned Dose Level _____			Ht _____ cm	Wt _____ kg	BSA _____ m ²		
Date Due	Date Given	Day	Pevonedistat mg	TEMO mg	IRIN mg	Cefixime mg	Studies
		PRE					a - m, n*, o, p
		1	mg				h, m, n*
		...					
		4					e
		5					
		6				mg	
		7				mg	
		8	mg	mg	mg	mg	b, e - h, m, n*
		9		mg	mg	mg	
		10	mg	mg	mg	mg	h, m, n*
		11		mg	mg	mg	
		12	mg	mg	mg	mg	e, h
		13				mg	
		14				mg	
		15				mg	b, e - h
		...					
		19					e
		...					
		22					b, e - h
		...					
		26/-1					e
		27/0				mg	
		28/1				mg	a - h, j - k, l^, p
			Following completion of Cycle 1, Cycle 2 starts on Day 28 or when starting criteria are met (see Section 5.3), whichever occurs later.				

* For consenting patients only.

^ Study may be obtained within 72 hours prior to the start of the subsequent cycle.

See [Section 6.0](#) for Dose Modifications for Adverse Events and [Section 7.0](#) and the COG Member website for Supportive Care Guidelines.

Version Date: 08/27/2020

Page 98

Required Observations in Cycle 1

All baseline studies must be performed within 7 days prior to enrollment unless otherwise indicated below. See [Section 8.0](#) for schedule of assessments.

- a. History
- b. Physical exam with vital signs: Vital signs should be checked prior to each pevonedistat infusion. Vital signs will be also be assessed at the end of treatment.
- c. Height, weight, BSA
- d. Performance status
- e. CBC, differential, platelets: Twice weekly during Cycle 1. If patients have Grade 4 neutropenia or thrombocytopenia, CBCs should be checked at least every other day until recovery to Grade 3 or until the criteria for dose limiting toxicity are met.
- f. Electrolytes including Ca⁺⁺, PO₄, MG⁺⁺
- g. Creatinine
- h. ALT, AST, bilirubin: Check prior to each dose of pevonedistat, then weekly for remaining weeks of cycle. If patients have Grade 2, 3, or 4 ALT/AST/bilirubin on or after Cycle 1 Day 8, AST/ALT/bilirubin should be checked at least every other day until recovery to ≤ Grade 1. See [Section 6.2.4](#) for more details.
- i. ECHO/EKG
- j. Albumin, Pulse Oximetry

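### The therapy delivery maps in Appendix XIII allow the next cycle to start one day earlier than the schema and Section 5.1 do, which in one reading shortens the cefixime course

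*Combined protocol and SAP*

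**What the plan says.** **Protocol body.** The Experimental Design Schema and Section 5.1 both state: "Days 27 and 28 of Cycle 1 are the same as Days -1 and 0 of Cycle 2". For later cycles Section 5.1 states: "Days 20 and 21 of Cycles 2+ are the same as Days -1 and 0 of subsequent cycles". Section 5.3 gives the lengths: "After Cycle 1 which is 28 days, a cycle may be repeated every 21 days".

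**Cefixime.** Section 5.1 requires: "Cefixime will be administered starting at least two days prior to the start of irinotecan", continuing during irinotecan and for "3 days after the last dose of irinotecan of each cycle for a total of at least 10 days".

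**Appendix XIII-A (Cycle 1 map).** The header says "Cycle 1 lasts 28 days". The last three rows are labelled 26/-1, 27/0 and 28/1, and the line under the table reads: "Following completion of Cycle 1, Cycle 2 starts on Day 28 or when starting criteria are met". That sentence continues with a reference to Section 5.3 and says that the later of the two applies, so Day 28 is the earliest permitted start.

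**Appendix XIII-B (Cycles 2+ map).** It states a length of 21 days, labels its last rows 19/-1, 20/0 and 21/1, and gives Day 21 as the earliest start, with the same clause.

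**The concern.** The body and the maps give two different days for the start of the next cycle. If Day 28 is Day 0 of Cycle 2, Cycle 2 begins on Day 29; the map allows Day 28. If Day 21 is Day 0 of the next cycle, that cycle begins on Day 22; the map allows Day 21.

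The maps are working forms. Sites complete and upload one for every cycle, so an incorrect start day there can reach practice. What is at stake is the antibiotic lead-in before irinotecan, which the protocol uses to prevent diarrhea. If chemotherapy moves forward by a day while cefixime stays on its printed days, the lead-in loses a day and the course falls below the stated minimum.

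**Working it through.** **Inputs**
- Cycle lengths: 28 days (Cycle 1) and 21 days (Cycles 2+), from Sections 5.1 and 5.3 and from the headers of both maps.
- Day mapping: schema and Section 5.1.
- Row labels, cefixime cells and start sentences: Appendices XIII-A and XIII-B.
- Cefixime in Cycles 2+: Days -1 to 8, with irinotecan on Days 1-5 (Section 5.1).
- Number of cycles: up to 17 (Sections 5.1 and 10.1).

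**1. The plan's own cefixime figure.** Lead-in 2 (Days -1, 0) + irinotecan 5 (Days 1-5) + follow-on 3 (Days 6-8) = 10 days. This reproduces the stated minimum.

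**2. Start of the next cycle.** If the last day L is Day 0, the next Day 1 is L + 1, and the cycle length is the next Day 1 minus 1.
- Body: 28 + 1 = Day 29, length 28; 21 + 1 = Day 22, length 21.
- Maps: Day 28, length 28 - 1 = 27; Day 21, length 21 - 1 = 20.

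The body reproduces the stated lengths. The maps fall one day short of the lengths in their own headers.

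**3. Cefixime cells.** In XIII-A, Days 27 and 28 have cefixime cells and Day 26 has none. In XIII-B, Days 20 and 21 have cells and Day 19 has none. Under the body's mapping these cells are Days -1 and 0, as required. Under the maps' labels they are Days 0 and 1, and the row labelled -1 has no cefixime, although XIII-B lists Day -1 as a cefixime day.

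**4. Consequence by reading.** Cefixime ends on Day 8 of the new cycle, which is the start day + 7.

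| Reading | Start | Cefixime days | Lead-in | Total |
|---|---|---|---|---|
| (a) Map start, cefixime on the end-of-cycle rows | Day 28 | 27-35 | 1 | 9 |
| | Day 21 | 20-28 | 1 | 9 |
| (b) Map start, cefixime on XIII-B's Day -1 and Day 0 rows | Day 28 | 26-35 | 2 | 10 |
| | Day 21 | 19-28 | 2 | 10 |
| (c) Section 5.1 | Day 29 | 27-36 | 2 | 10 |
| | Day 22 | 20-29 | 2 | 10 |

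Only (a) falls short, by one lead-in day and one course day. Reading (b) needs cefixime on Day 26 or 19, where the end-of-cycle rows have no cell.

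**5. Total duration.** Seventeen cycles have 17 - 1 = 16 transitions.
- Body: 28 + 16 × 21 = 364 days.
- Maps, no delay at any transition: 27 + 15 × 20 + 21 = 348 days. The last cycle keeps 21 days because no cycle follows it. Check: 364 - 16 = 348.

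**The case against.** **The start day is only the earliest one.** The maps take the later of Day 28 (or 21) and the day the starting criteria are met, and they point to Section 5.3. This stands as mitigation. It does not remove the conflict, because a patient who meets the criteria in time may still start on Day 28 or 21.

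**A shortfall requires a site to overlook other instructions.** These are the lead-in and course minimum in Section 5.1, the explicit day mapping there and in the schema, and XIII-B's own Day -1 and Day 0 cefixime rows. Both maps refer to Section 5.1 for treatment details. XIII-A also calls its chart an example, although that remark concerns the scheduling of observations and XIII-B has no such remark. This stands, and it keeps the point minor.

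**Not every feature of the rows helps to show which version is wrong.** A reader might take the missing chemotherapy cells in rows 28/1 and 21/1 as proof that these cannot be Day 1, but the next cycle's doses would be recorded on the next form anyway. The studies listed there are weak evidence too: many may be done within 72 hours before the cycle, and liver tests are also listed on dosing days. XIII-B's footnote, which assigns Days -1 and 0 to the last two days of the previous cycle, conflicts with the labels only once the 28- or 21-day length is assumed. The case rests on the body text, the stated lengths and the cefixime cells.

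**Stronger inferences are not supported.** A reader might infer that the sponsor chose cycles of 27 and 20 days; the maps' own headers say 28 and 21. A reader might infer that the DLT window or the delay-based DLT criteria change. Section 5.6 ties the window to Cycle 1, which is 28 days throughout, and its delay criteria give a length of delay without using the maps.

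**Conclusion.** The inconsistency is real and minor. Both maps place the earliest start of the next cycle one day before the day that follows from the schema, Section 5.1 and the maps' own stated lengths.

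The cost arises in one of three readings: 1 lead-in day instead of at least 2, and 9 course days instead of at least 10, per transition, at up to 16 transitions. That maximum assumes a patient who completes all 17 cycles, no delayed start, and a site that follows reading (a) every time. If every transition followed the maps without delay, 17 cycles would last 348 days instead of 364.

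A reader might infer that patients will have more diarrhea. The documents give no figure for the effect of one lead-in day, so that cannot be claimed. The lead-in within Cycle 1 (Days 6-7 before irinotecan on Day 8) is correct everywhere, so only Cycles 2+ are affected. No endpoint, decision-rule or sample-size figure changes.

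**What to change.** - **Appendix XIII-A:** relabel the last two rows 27/-1 and 28/0, remove the -1 label from Day 26, and give Day 29 as the earliest start of Cycle 2.
- **Appendix XIII-B:** relabel the last two rows 20/-1 and 21/0, remove the -1 label from Day 19, and give Day 22 as the earliest start of the next cycle.
- **Both:** keep the condition that the starting criteria must be met and that the later day applies.

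The cost is three row labels and one sentence in each of two appendix tables. The protocol body needs no change.

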APPENDIX XIII-B: THERAPY DELIVERY MAPS (TDMS) FOR ALL SUBSEQUENT CYCLES

Therapy Delivery Map – All Subsequent Cycles		Accession #

This Therapy Delivery Map (TDM) relates to all subsequent cycles (Cycles 2+). Each cycle lasts 21 days. This TDM can be used for all dose levels of pevoneditat. Please record the dose level in the chart below. Treatment may continue in the absence of disease progression or unacceptable toxicity. A cycle may be repeated 17 times, up to a total duration of therapy of 12 months. Use a copy of this page once for each cycle (please note cycle number below). This form is to be completed and uploaded into RAVE at the end of every cycle.
		Patient COG ID number
		Institution

Criteria to start each cycle are listed in [Section 5.3](#). Extensive treatment details are in [Section 5.1](#).

This TDM is on 3 pages.

DRUG	ROUTE	DOSAGE	DAYS	IMPORTANT NOTES
Cefixime	PO	8 mg/kg/dose daily	-1 to 8, 20-21	Maximum dose is 400 mg/day.
Temozolomide (TEMO)	PO	100 mg/m ² /dose daily	1-5	Maximum dose is 200 mg/day. See Appendix IV for oral capsules dosing nomogram.
Irinotecan (IRIN)	IV over 90 minutes	- If BSA < 0.6 m ² : BSA-based dosing (See Section 5.1 dosing table) - If BSA ≥ 0.6 m ² : 50 mg/m ² /dose daily	1-5	Administer one hour after temozolomide.
Pevonedistat IND # 136078	IV over 60 minutes	Dose Level -1: 10 mg/m ² Dose Level 1: 15 mg/m ² Dose Level 2: 20 mg/m ² Dose Level 3: 25 mg/m ² Dose Level 4: 35 mg/m ²	1, 3, 5	Administer immediately after irinotecan. If pevoneditat is delayed, a minimum of 1 calendar day between any 2 doses should be maintained. A maximum of 3 doses of pevoneditat per Cycles 2+ should not be exceeded.

NOTE: PCP prophylaxis should start on Cycle 1 Day 8, given twice daily for 3 consecutive days a week (i.e., BID Friday, Saturday, Sunday), every week or per institutional practice, until the end of protocol therapy. See [Section 5.1](#) for details.

Cycle #	Assigned Dose Level	Ht	cm	Wt	kg	BSA	m ²
Date Due	Date Given	Day	Pevonedistat mg	TEMO mg	IRIN mg	Cefixime mg	Studies
Enter calculated dose above and actual dose administered below							
		-1*				mg*	
		0*				mg*	a - d, h, j - k
		1	mg	mg	mg	mg	
		2		mg	mg	mg	
		3	mg	mg	mg	mg	h
		4		mg	mg	mg	
		5	mg	mg	mg	mg	h
		6				mg	
		7				mg	
		8				mg	e - g, h
		...					
		15					e - g, h
		...					
		19/-1					
		20/0				mg	
		21/1				mg	a - d, h, j - k, l#, p
			Following completion of this cycle, the next cycle will start on Day 21 or when starting criteria are met (see Section 5.3), whichever occurs later.				

End of Cycle 2, then every other cycle x 2 then q 3 cycles

*Cefixime on these days should be reported as the last two days of the previous cycle.

See [Section 5.0](#) for Dose Modifications for Adverse Events and [Section 7.0](#) and the COG Member website for Supportive Care Guidelines.

Required Observations in All Subsequent Cycles

All baseline studies must be performed within 7 days prior to enrollment unless otherwise indicated below. See [Section 8.0](#) for schedule of assessments.

- a. History[^]
- b. Physical exam with vital signs[^]: Vital signs should be checked prior to each pevonedistat infusion. Vital signs will also be assessed at the end of treatment.
- c. Height, weight, BSA[^]
- d. Performance status[^]
- e. CBC, differential, platelets: If patients develop Grade 4 neutropenia, CBCs should be checked every 3 to 4 days until recovery to Grade 3. If patients remain on study for > 4 cycles and ≥ 4 cycles and ≥ Grade 3 cytopenias are not observed, then CBCs may be obtained at the start of subsequent cycles and as clinically indicated.
- f. Electrolytes including Ca++, PO4, MG++[^]
- g. Creatinine[^]
- h. ALT, AST, bilirubin*: Check prior to each dose of pevonedistat, then weekly for remaining weeks of cycle. If patients have Grade 2, 3, or 4 ALT/AST/bilirubin on or after Cycle 1 Day 8, AST/ALT/bilirubin should be checked at least every other day until recovery to ≤ Grade 1. See [Section 6.2.4](#) for more details.
- i. ECHO/EKG
- j. Albumin[^]; Pulse Oximetry
- k. Pregnancy test[^]: Women of childbearing potential require a negative pregnancy test prior to starting treatment; sexually active patients must use an acceptable method of birth control. Abstinence is an acceptable methods of birth control. All women of childbearing potential must have a pregnancy test done every cycle prior to initiation of a new cycle.
- l. Tumor disease evaluation⁵: Tumor disease evaluation should be obtained on the next consecutive cycle after initial documentation of either a PR or CR. If the institutional investigator determines that the patient has progressed based on clinical or laboratory evidence, he/she may opt not to confirm this finding radiographically.
- m. Pharmacokinetics (required): See [Section 8.3](#) for details.
- n. Pharmacodynamics (optional): See [Section 8.4](#) for details.
- o. INR
- p. Bone marrow evaluation. With tumor disease evaluation; end of cycle 2, then every other cycle x2, then every 3 cycles. If a solid tumor patient is suspected to have or has a history of bone marrow involvement then a pre-study bone marrow biopsy and/or aspirate is required. This should then be repeated with each tumor disease evaluation if pre-study bone marrow was positive for metastatic disease.

[^] Studies may be obtained within 72 hours prior to the start of the subsequent cycle.

This listing only includes evaluations necessary to answer the primary and secondary aims. OBTAIN OTHER STUDIES AS REQUIRED FOR GOOD CLINICAL CARE.

Comments

(Include any held doses, or dose modifications)
